## OBJECTIVES

Specific Aim 1: To quantify and compare the neuromuscular, cardiopulmonary responses and gait kinematics during walking with and without C-brace in individuals with hemiparesis or hemiplegia. We plan to recruit patients with hemiparesis or hemiplegia following stroke and include a wide range of gait impairments. It is expected that subjects will demonstrate various degree of difference in energy expenditures, neuromuscular responses, functional status and gait characteristics between walking with and without C-brace, depending on their current walking ability. We hypothesize that the changes in cardiopulmonary responses, neuromuscular responses of major lower muscle groups and gait characteristics would be greater in persons with lower functional status and severe gait impairment.

Specific Aim 2: To investigate the association between gait improvement (i.e. gait kinematics, speed and walking distance) in walking with C-Brace and baseline neuromuscular, cardiopulmonary characteristics that affect gait performance, cognition and physical function in individuals with hemiparesis or hemiplegia. We also aim to develop an algorithm to characterize and subgroup the patients who receive gait training with C-Brace. We hypothesize that the improvements observed in walking with C-Brace are related to muscle strength, range of motion, severity of spasticity and the functional status, and the degree of relations may be varied. We will then identify the key parameters and measures based on association to develop an algorithm to characterize the patients who may receive the maximal benefit of using C-Brace for walking.

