## STUDY DESIGN

### Subjects

15 individuals with diagnosis of stroke and residual hemiparesis or hemiplegia will be grouped into one of three categories based on their walking speed at baseline. Subjects will receive 4 weeks of gait training utilizing C-Brace, 3 times per week for a total of 12 sessions. We will utilize the 10 Meter Walk Test to assess gait speed for all groups at baseline (week 0). Once training sessions are complete and subject is considered an independent experienced user (week 5) we will assess the neuromuscular and cardiopulmonary responses and gait kinematics during walking with and without C-Brace. Subjects will then continue with use of C-Brace in their daily routine in their home and community environments for 4-6 weeks. Subjects will then return for a follow up visit (week 8-10) and reassessment of neuromuscular and cardiopulmonary responses and gait kinematics during walking with and without C-Brace.

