## **Study Population**

15 individuals with hemiparesis or hemiplegia after stroke in the Houston metropolitan area. Inclusion and exclusion criteria are listed in Table 1. Participants will be screened and evaluated by study investigators and certified physical therapists. We plan to recruit individuals with a wide range of walking abilities. The walking ability will be determined by gait speed from 10 meter walk test: severe gait impairment (gait velocity <0.4 m/s, moderate gait impairment (gait speed 0.4-0.8 m/s) and mild impairment (gait speed >0.8 m/s)[17].

Table 1:

	Inclusion Criteria	Exclusion Criteria
15 subjects (5 subjects in each group) • Mild • Moderate • Severe	

• Age 18 - 65 years

• Diagnosis of hemiparesis or hemiplegia following stroke

• Presence of abnormal walking pattern

• Poor knee control during stance phase

• Cognitive ability to (or care provider) manage daily charging of battery

• Cognitive ability to follow commands

• Hip flexor muscle strength grade 3 or greater or the ability to perform reciprocal gait using compensatory patterns

• Able to operate C-brace

	

• Weight > 275 lbs. (Includes body weight and weight of heaviest object carried)

• Less than 2° of ankle motion

• Severe spasticity of the quadriceps (MAS >3) and/or uncontrolled spasticity of the quadriceps

• Severe spasticity of other lower limb muscles (MAS >3)

• Fixed genuvalgum exceeding 10° beyond anatomic neutral valgum

• Any fixed genuvarum exceeding anatomic neutral varum.

• Hip or knee flexion contractures greater than 10°

• Presence of COPD

• Chronic heart failure – NYHA stages 3 and 4

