### **Specific Aim 1:**

To quantify and compare the neuromuscular, cardiopulmonary responses and gait kinematics during walking with and without C-brace in individuals with hemiparesis or hemiplegia. We plan to recruit patients with hemiparesis or hemiplegia following stroke who present with gait impairments. It is expected that subjects will demonstrate varying degrees of energy expenditures, neuromuscular responses, functional status and gait characteristics between walking with and without C-brace, depending on their current walking ability. We hypothesize that the changes in cardiopulmonary responses, neuromuscular responses of major lower muscle groups and gait characteristics will be greater in persons with lower functional status and more severe gait impairments.

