### **Outcome Measures:**

We will measure the following parameters during gait with and without C-Brace at completion of training sessions and at follow up.

- *Timed Up and Go:* Assesses mobility, balance, walking ability, and fall risk in older adults. The test measures the time it takes the subject to perform a sit to stand from a chair with arms, walk to a mark on the ground 10 feet away and return to the seated position in the chair with arms. This test has been used in assessing stroke recovery with high reliability and validity[18].
- *10 Meter Walk Test (10MWT):* Measure of gait speed. Subjects will walk a total of 14 meters at their preferred walking speed and at a fast pace. The test measures the time it takes the subject to complete the middle 10 meters of the walk.
- *Kinematics and electromyography (EMG):* Bilateral upper and lower extremity kinematics and surface electromyography (sEMG) recordings will be collected during 10MWT. Infrared light emitting diode markers will be attached to bilateral lower extremities. The marker data will be recorded using the NDI Optotrak Certus motion capture system. Marker data will be processed using custom Matlab program to

determine lower extremity joint excursion and joint angular velocities. For EMG, we will place bipolar surface electrodes on the bilateral major leg muscles to record electromyography (1000Hz, Motion Labs 16-Channel EMG System). We will calculate the EMG amplitude and burst duration over the whole gait cycle during the 10MWT.

- *Six-minute walk test (6MWT):* This test assesses distance walked over 6 minutes as a sub-maximal test of aerobic capacity/endurance. It has good responsiveness to detect improvements in capacity to walk in stroke patients [19].
- *Metabolic expenditure during walking:* Oxygen consumption during 6MWT will be determined using a portable metabolic system. Metabolic data will be collected on a breath-by-breath basis during gait assessment. Prior to the testing, the system will be calibrated using room air and reference gas mixture. During the testing, the subject will wear the face mask at all times and will be asked to breathe normally. Subjects will also wear a heart rate monitor. The data will be synchronized with kinematic and electromyography data for further analysis. This task will be performed during walking with and without C-Brace.

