## STATISTICS

### Aim 1:

The effects of C-Brace on dependent variables will be analyzed using separate 2-factor (group x condition) analyses of variance (ANOVA) with repeated measures on the walking condition (walking with and without C-Brace). The model will first test for the interaction to determine if 3 groups (mild, moderate and severe) respond similarly across time. In the event of a significant interaction ( $p < .05$ ) we will test for differences between among groups at each point in time (post hoc Tukey).

[figure not shown]

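### The Aim 1 post hoc Tukey test reads as comparing group levels, so no planned test or interval shows which severity group changes most with C-Brace

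*Combined protocol and SAP*

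**What the plan says.** OBJECTIVES (Specific Aim 1) hypothesises that changes in cardiopulmonary, neuromuscular and gait measures "would be greater in persons with lower functional status and severe gait impairment". STUDY PROCEDURES (Specific Aim 1) repeats this: changes in "gait characteristics will be greater in persons with lower functional status and more severe gait impairments". The hypothesis therefore concerns a change, and it has a direction.

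Subjects are "grouped into one of three categories based on their walking speed at baseline" (STUDY DESIGN, Subjects). Study Population adds: "The walking ability will be determined by gait speed from 10 meter walk test". The bands are below 0.4, 0.4–0.8 and above 0.8 m/s, with 5 subjects in each (Table 1). The 10 Meter Walk Test is also an Aim 1 outcome. On timing, Outcome Measures under Specific Aim 1 says: "We will measure the following parameters during gait with and without C-Brace at completion of training sessions and at follow up".

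STATISTICS (Aim 1) plans a two-factor ANOVA for each outcome, with severity group between subjects and walking condition as the only repeated factor. The interaction is to show whether the "3 groups (mild, moderate and severe) respond similarly across time". If it is significant at p < .05, "we will test for differences between among groups at each point in time (post hoc Tukey". The section names no contrast of the change between groups, no brace effect within a group and no confidence interval.

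**The concern.** With three groups the interaction test has 2 numerator degrees of freedom and no direction. A significant result says that the brace effect is not the same in all groups, and the follow-up has to show where. Comparing groups within each walking condition answers another question: whether severe, moderate and mild walkers differ in level. Because the groups were formed on baseline gait speed, severe and mild will usually differ in level on that outcome whichever of them gains more. A report that severe differs from mild could then be misread as support for the Aim 1 hypothesis.

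The wording adds to the difficulty. The model has no time factor, yet both the interaction sentence and the follow-up sentence speak of time, and with/without data are collected at two visits.

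Aim 2 does not fill the gap. Its regressions predict changes in gait speed and distance from strength, range of motion, spasticity, Fugl-Meyer and Berg scores. They do not use the severity groups and do not cover EMG, kinematics or oxygen use.

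**Working it through.** The documents give no SD, effect size or power figure, so there is nothing of the plan's own to reproduce. Design inputs taken from the documents are 3 groups, 5 per group, 2 conditions, alpha 0.05 and the speed bands.

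**What the interaction tests.** With two conditions, the group-by-condition interaction is a one-way ANOVA on each subject's with-minus-without difference. Residual degrees of freedom are 3 × (5 − 1) = 12, and the critical value F(2, 12) is 3.885. This is a valid test of the hypothesised quantity, but it is non-directional.

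**Precision of the missing contrast.** Assume a brace-effect SD of 0.10 m/s and a visit measurement SD of 0.08 m/s.
- If visit error is shared between conditions, the SD of the difference is 0.10. If it is independent, the SD is √(0.10² + 2 × 0.08²) = 0.151.
- Tukey-adjusted 95% half-width for a between-group difference in change, with q(0.05; 3, 12) = 3.773: 3.773 × 0.10/√5 = 0.169, or 3.773 × 0.151/√5 = 0.255 m/s.
- Within-group 95% half-width, t(0.975, 12) × SD/√5: 0.097 or 0.147 m/s.

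**Level comparison against change comparison.** Simulation of gait speed, 40,000 runs per scenario. Assumed underlying speeds are uniform on 0.1–0.4, 0.4–0.8 and 0.8–1.2 m/s, with the SDs above. In the table, *levels* means that Tukey finds severe different from mild in both conditions. All percentages except the second column are among runs with a significant interaction, as the plan requires. Ranges cover independent and shared visit error. The *+0.15* and *+0.25* columns add that between-subject SD (m/s) since baseline, so that the bands overlap.

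| Mean gain, mild/moderate/severe (m/s) | Interaction significant (independent / shared) | Levels | Levels, +0.15 | Levels, +0.25 |
|---|---|---|---|---|
| 0.20/0.10/0 | 36% / 70% | 100% | 100% | 90–92% |
| 0/0.10/0.20 | 36% / 70% | 98–99% | 80–84% | 51–56% |
| 0/0.15/0.30 | 69% / 97% | 91–93% | – | – |
| 0/0.20/0.40 | 92% / 100% | 72–73% | 43–45% | 23–24% |
| 0/0.20/0 | 46% / 83% | 100% | 99% | 86–87% |

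At a 0.20 gap, Tukey on the differences separates severe from mild in the right direction in 86–96% of these runs and in the wrong direction in about 0%. In the last row, where severe and mild gain equally, it separates them in 2–5%. The added spread leaves these figures unchanged because it is common to both conditions and cancels in the difference.

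With equal gains in all groups the interaction is significant in only about 5% of runs, so nothing is claimed for that case.

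**Second set of assumptions.** Level means 1.0/0.6/0.3 m/s (mild/moderate/severe), between-subject SD 0.10–0.15, SD of change 0.10, 100,000 runs. Given a significant interaction, the level test finds mild above severe in both conditions in 92–99% of runs when severe gain 0.20 more, and in about 100% when mild do. Tukey on the change gives the right direction in about 96% and the wrong direction in 0.0%.

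**The case against.** The strongest reply concerns the reading. The plan says time, not condition, and there are two real time points at which both conditions are measured. The sentence before the follow-up is about how groups respond. On that view the post hoc step could mean comparing brace effects among groups at each visit, which is the contrast wanted. This reading is possible. But the sentence never names the change as the quantity compared, and in a repeated-measures ANOVA such wording normally means group means at each level of the repeated factor. Text that supports two different analyses needs correcting under either reading.

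Second, the cell means already show direction. When gains rise or fall steadily with severity by 0.20 m/s, a significant interaction comes with the correct severe-versus-mild ordering in at least 99.9% of runs. That stands, but only as description. When only the moderate group gains, the ordering of severe and mild is a coin flip, and a formal contrast is needed.

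Third, the level test is not blind to a closing gap. With more spread and a larger gain in the severe group, severe and mild differ in both conditions in as few as 23–24% of runs, and often differ only without the brace. This stands too. Even so, severe differs from mild in at least one condition in about 92–100% of significant-interaction runs in every unequal-gain scenario examined, so the result still does not measure the change.

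Finally, the illustration is for gait speed. The argument extends to the six-minute walk and Timed Up and Go, but no figure in the documents supports it for EMG, kinematics or oxygen use. The lack of a change contrast, by contrast, applies to every Aim 1 outcome and depends on no assumed number.

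**Conclusion.** The concern holds. The interaction test is sound, and comparing groups within a condition is a legitimate secondary question, so the follow-up is incomplete rather than invalid. As most naturally read, however, no planned Aim 1 test or interval says which group's change is larger, and that is what the hypothesis is about.

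For gait speed under the base assumptions, opposite truths (mild gaining 0.20 m/s more, or severe gaining 0.20 m/s more) give the same level result in 98–100% of significant-interaction runs. That agreement weakens as subjects spread out after baseline. The missing interval would be about ±0.17 to ±0.25 m/s between groups. That is wide, and a reason to show it. These sizes rest on assumed SDs and gains; the mismatch between hypothesis and follow-up rests on the text alone. It should be fixed before analysis.

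**What to change.** In STATISTICS (Aim 1), make the interaction sentence refer to responses across walking conditions instead of time, and replace the post hoc sentence with wording such as:

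*The with-minus-without C-Brace difference will be computed per subject for each outcome. After a significant group x condition interaction (p < .05), groups will be compared on this difference by Tukey-adjusted pairwise comparisons. Between-group differences in change (Tukey-adjusted 95% CIs) and the mean change within each group (95% CI) will be reported whether or not the interaction is significant. One visit (post-training or follow-up) will be named in advance as the main analysis, and the other reported as supportive.*

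The documents support either visit: post-training comes after 12 sessions, follow-up after 4–6 weeks of home use. Naming a main visit goes beyond the core correction, but it settles what the references to time mean and avoids a second full set of tests. An ordered contrast across severity would be a reasonable alternative to Tukey, since the hypothesis is ordered.

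The cost is wording in one section, with the same visits, data and software. Reporting grows slightly, and the comparison of group levels within each condition becomes secondary or descriptive.

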### Aim 2:

Pearson product-moment correlation coefficients will be used to examine relationships among muscle strength, range of motion, spasticity, scores in Fugl-Meyer assessment and Berg Balance Scale. Hierarchical regression analyses will then be conducted to determine whether changes in gait speed and distance could be predicted on the basis of muscle strength, range of motion, spasticity, scores in Fugl-Meyer assessment and Berg Balance Scale. The order of entry will be based on presumed causal priority and to allow removal of confounding variables.

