### **Specific Aim 2:**

To investigate the association between the gait improvement (i.e. gait speed and walking distance) in walking with C-Brace and baseline neuromuscular, cardiopulmonary characteristics that affects gait performance, cognition and physical function in individuals with hemiparesis or hemiplegia. We also aim to develop an algorithm to characterize the patients who may receive the maximal benefit of using C-Brace for walking. We hypothesize that the improvements observed in walking with C-Brace are related to muscle strength, range of motion, severity of spasticity and the functional status and the degree of relations may be varied. We will then identify the key parameters based on association to develop an algorithm to characterize the patients who may receive the maximal benefit of using C-Brace for walking.

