### **Outcome Measures:**

The following assessments will be measured at baseline and follow-up (without wearing C-brace):

- *Folstein Mini Mental State Examination (MMSE):* Mini Mental State Examination provides information about orientation, attention, learning, calculation, delayed recall, and construction. Several studies report acceptable validity of MMSE as a screening instrument and its relationship to functional outcome in stroke population[20].
- *Lower limb muscle strength and range of motion:* Muscle strength will be measured and quantified by using dynamometers on major bilateral lower limb muscles such as hip flexors and extensors, hip abductors and adductors, knee flexors and extensors and ankle dorsiflexors and plantarflexors. Range of motion will be measured on bilateral hip, knee and ankle joints using goniometry.
- *Fugl-Meyer Assessment – Lower Extremity and Balance:* This test evaluates and measures recovery of movement in individual post stroke. Fugl-Meyer has been used in both clinical and research settings and is one of the most widely used quantitative measures of motor impairment [21]. It uses an ordinal scale for scoring of 17 items for

the lower limb component and 7 items on the Balance component of the F-M scale (0: cannot perform; 1: can perform partially; 2: can perform fully).

- *Modified Ashworth Scale (MAS)*: This test measures spasticity in patients with lesions of the Central Nervous System by testing resistance to passive movement about a joint with varying degrees of velocity. Scores range from 0-4, with 6 choices (i.e., 0, 1, 1+, 2, 3, 4), with 0 indicating normal muscle tone, and 4 indicating very high spasticity. We will measure spasticity in lower limbs.
- *Timed Up and Go (TUG) Test*: Assesses mobility, balance, walking ability, and fall risk in older adults. This test has been used in assessing stroke recovery with high reliability and validity [18]. The test measures the time it takes the subject to perform a sit to stand from a chair with arms, walk to a mark on the ground 10 feet away and return to the seated position in the chair with arms.
- *Berg Balance Scale (BBS)*: A 14-item objective measure designed to assess static balance and fall risk in adult populations, with maximum summed score of 56 (higher scores represent better functional outcome). This test has been widely used to measure functional recovery in stroke patients with high reliability [22].

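### The Aim 2 regression fits five domains in 15 subjects with no internal validation, no stated entry order and no baseline gait term named, yet it sets the order of the algorithm's elements

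*Combined protocol and SAP*

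**What the plan says.** Study Population, Table 1, sets the sample at "15 subjects (5 subjects in each group"). STATISTICS, Aim 2, plans hierarchical regressions of change in gait speed and in distance, to see whether they "could be predicted on the basis of muscle strength, range of motion, spasticity, scores in Fugl-Meyer assessment and Berg Balance Scale". Order of entry is to follow an assumed causal ranking and to let confounders be removed. Neither the ranking nor any confounder is named.

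The Aim 2 outcome measures collect several values in most of these domains. Strength covers both sides for muscles such as "hip flexors and extensors, hip abductors and adductors, knee flexors and extensors and ankle dorsiflexors and plantarflexors". Range of motion covers hip, knee and ankle on both sides. Spasticity is graded at unlisted lower-limb sites, and Fugl-Meyer has a lower-extremity part and a balance part. Only the Berg scale has a stated summed score (maximum 56).

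Three places bear on what change means:
- Specific Aim 2 targets "the gait improvement (i.e. gait speed and walking distance) in walking with C-Brace".
- Its outcome list, which includes the 10-metre and six-minute walk tests, opens: "The following assessments will be measured at baseline and follow-up (without wearing C-brace").
- The Aim 1 list, with the same two tests, states: "We will measure the following parameters during gait with and without C-Brace at completion of training sessions and at follow up".

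On baseline gait, Study Design states: "We will utilize the 10 Meter Walk Test to assess gait speed for all groups at baseline (week 0"). The Assessment Timeline also has both walk tests at the baseline visit. Neither is listed as a regression term.

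The Clinical Algorithm section derives the algorithm and the order of its elements from the regression. It leaves the minimal criteria for each element to a larger study.

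**The concern.** Five predictors in 15 subjects is three subjects per predictor. A least-squares fit of that size explains a good share of the variance by chance, so in-sample R-squared can look useful when the equation predicts a new subject no better than the mean does. The plan names no figure to report and no check such as leave-one-out or bootstrap.

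The result is then used. Developing the algorithm is part of the study's stated purpose, and the Background suggests that the predictors could serve as entry criteria for later trials. An order of elements that reflects noise, or an entry sequence chosen after seeing the data, could be carried forward.

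Baseline gait matters because OBJECTIVES expects that changes in cardiopulmonary and neuromuscular responses and "gait characteristics would be greater in persons with lower functional status and severe gait impairment", and Study Population grades impairment by walking speed. A domain score may therefore predict change only because it tracks baseline speed. It would still be a valid predictor, but the plan would not show whether it adds to a speed test already performed.

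**Working it through.** The plan gives no power, target R-squared or sample-size derivation for Aim 2, so there is no stated figure to reproduce.

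**Inputs.** n = 15 (Study Population); k = 5 domains (STATISTICS, Aim 2). Alpha 0.05 is assumed for Aim 2, because the plan states it only for the Aim 1 interaction.

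**Number of measurements.** Strength 8 groups x 2 sides = 16; range of motion 3 joints x 2 sides = 6; spasticity at least 1; Fugl-Meyer 2; Berg 1. The total is at least 26. The 16 strength values alone exceed the n - 1 = 14 degrees of freedom, so some reduction has to be chosen. The best case is one score per domain, leaving 15 - 1 - 5 = 9 residual df.

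**No true association (closed form).**
- Mean R-squared = k/(n - 1) = 5/14 = 0.357.
- R-squared follows Beta(k/2, (n - 1 - k)/2) = Beta(2.5, 4.5), so P(R-squared >= 0.5) = 0.209.
- Critical R-squared = kF/(kF + 9) with F(0.95; 5, 9) = 3.48: 17.4/26.4 = 0.659.
- An observed R-squared of 0.50 has p = 0.21 and adjusted R-squared 1 - 0.5 x 14/9 = 0.22.

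**Some true association (simulation).** Assumptions: normal predictors, pairwise correlation 0.3-0.6, true weights 5:4:3:2:1. The leave-one-out denominator uses the leave-one-out mean; values with the ordinary total sum of squares are in brackets.

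| True R-squared | Mean in-sample | Mean adjusted (SD) | Median leave-one-out |
|---|---|---|---|
| 0.25 | 0.50 | 0.23 (0.28) | about -0.27 (about -0.45) |
| 0.50 | 0.66 | 0.47 (0.24) | about +0.16 (about 0.04) |

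At true R-squared 0.25, leave-one-out R-squared is below zero in about 70% of trials.

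**Order of elements, true R-squared 0.50, correlation 0.3-0.6.** Share of trials in which the truly strongest predictor ranks first (chance is 1/5 = 20%):

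| Ranking statistic | Assumed weights | Strongest ranks first |
|---|---|---|
| Coefficient, t or simple correlation | 5:4:3:2:1 | 29-36% |
| Same | each half the one before | 43-61% |
| Same | one predictor carries everything | 73-91% |
| R-squared increment, strongest entered first | 5:4:3:2:1 | about 65-80% |
| R-squared increment, strongest entered last | 5:4:3:2:1 | about 5-13% |

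The last two rows use the same data and the same true effects; only the entry order differs.

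**Precision of one adjusted association.** For an observed partial r of 0.50 with one covariate, Fisher's z is 0.549 and its standard error is 1/sqrt(15 - 1 - 3) = 0.302. The limits on the z scale are -0.042 and 1.140, so the 95% CI for r is -0.04 to 0.81.

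**The case against.** The best defence is that this is a small exploratory study that already calls its characteristics hypothesised and asks for a larger study before any cut-off is set. That stands for the cut-offs, but the sentence does not reach the order of elements or any choice of elements drawn from the regression.

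A reader might infer that a wrong order would misclassify patients. The documents do not support that. The Clinical Algorithm section speaks of a subject meeting the minimal criteria of the elements. If all must be met, their order may not change who is classed as benefiting. Figure 1 is not shown in the text reviewed, so this cannot be checked, and the elements themselves may be fixed in advance.

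A reader might also infer that no domain has a single score, or that all 26 measurements enter separately. Berg has a summed score, and the plan names five domains without saying that each muscle enters. The gap concerns strength, range of motion and spasticity, and partly Fugl-Meyer.

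The ranking percentages rest on assumed weights and on ranking statistics that the plan does not name; a single dominant predictor would usually be found. This objection stands, and it is why the range is shown. The null results need no assumed effect size.

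The sentence on removing confounders would allow a baseline gait term, but it names none. Lacking that term does not invalidate a predictor; it leaves the question of added value unanswered. Finally, adjusted R-squared and the F-test can be computed from the same fit, but the plan commits to neither, and neither shows how the equation predicts a new subject.

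**Conclusion.** The concern holds in a limited form. Followed as written, Aim 2 yields a heavily overfitted model, and the order of the algorithm's elements is taken from it without the caution already given to the minimal criteria. The overfitting is firm: with no association, an average in-sample R-squared of 0.36 and a 21% chance of 0.5 or more follow from n = 15 and k = 5 alone. These figures assume one score per domain and no dropout.

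How poorly the model would predict depends on the unknown true R-squared: leave-one-out performance is typically negative at 0.25 and modestly positive at 0.50. It would go too far to say that the regression can find nothing. How poorly the order would be recovered depends on the assumed weights and on the ranking statistic. If increments are used, the unspecified entry order largely decides the result.

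The effect of a wrong order on patient classification is unproven. The point is worth acting on because the remedy is cheap and changes what Aim 2 can claim.

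**What to change.** In STATISTICS, Aim 2:
1. Fix in advance the order of entry, one score per domain, and the visits and brace condition that define change.
2. Report leave-one-out R-squared (stating its denominator) and adjusted R-squared with the overall F-test, not in-sample R-squared alone.
3. Report each candidate's association with change, with a 95% CI, both unadjusted (does it predict change?) and adjusted one candidate at a time for baseline 10-metre speed or six-minute distance (does it add to baseline gait?). Present these as estimates, without selection by significance.

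In Clinical Algorithm: extend the larger-study sentence so that the order of elements, and any choice of elements drawn from the regression, is also described as hypothesis-generating.

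Cost: wording and a little more analysis. No new subjects, visits or data are needed, since both walk tests are already scheduled at baseline. The downside is less impressive figures and possibly no clear order. The change makes the uncertainty visible; it does not make an order reliable in 15 subjects.
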